7.2 Toxicity Management

Talimogene laherparepvec administration can cause side effects, which may include all, some, or none of the following. However, the side effects are not limited to the following lists.

- Very Common side effects (>10% of subjects):
 - Flu-like illness
 - Injection site pain
 - Headache
 - Joint pain
 - Arm or leg pain
 - Diarrhea
 - Constipation
- Common side effects (1-10% of subjects):
 - Injection site reactions
 - Cellulitis
 - Wound complication at the injection site (secretion or discharge)
 - Pain or discomfort
 - Cold sore or fever blister in mouth
 - Anemia
 - Malaise
 - Weight loss
 - Dehydration
 - Bruise
 - Dizziness
 - Flushing
 - Rash
 - Dermatitis
 - Deep vein thrombosis
 - Autoimmune reactions
- Uncommon side effects (less than 1% of subjects):
 - Injection site reactions
 - Herpetic keratitis
 - Angioedema
 - Plasmacytoma
 - Delayed wound healing at the site of injection

Reactions at or near the area of the injection have been seen in other people administered talimogene laherparepvec. Symptoms include bleeding, redness, swelling and inflammation at the injection site. Skin infection caused by bacteria at the site of injection which may require hospitalization for antibiotic treatment have also been reported. Other symptoms may include warmth at the injection site or symptoms of delayed wound healing at or around the injection site such as injection site discharge, foul odor, or dead tissue at the injection site. If you notice symptoms of delayed wound healing at the injection site(s), you should contact the study doctor or his/her staff immediately.

Talimogene laherparepvec contains genetic material that makes human Granulocyte Macrophage Colony-Stimulating Factor (GM-CSF). Known side effects of human GM-CSF include, but are not limited to, musculoskeletal pain, fever, chills, shortness of breath, rash, fatigue, gastrointestinal effects, and fluid around heart and lungs. Although the amount of human GM-CSF released when treating melanoma lesions with talimogene laherparepvec is very small, these side effects may still occur.

Management of any toxicity related to talimogene laherparepvec administration or study may involve holding therapy until patients have recovered from any talimogene laherparepvec- or study-related adverse events. The management of the above known and other toxicity not listed above is largely based upon supportive care and institutional standards in managing these conditions. The management is at the discretion of the treating physician. If deemed appropriate, the treating physician may seek out subspecialty medical care of the patients, e.g. ophthalmologic evaluation for suspected herpetic keratitis, dermatologic consult for skin lesions that need specialist evaluation, or infectious disease consult for suspected herpes infections. Supportive medications may be employed at the discretion of the treating physician to support a patient through symptoms experienced as a result of the toxicity, e.g. pain medications for pain, anti-diarrheal agents for diarrhea, stool softeners and laxatives for constipation, anti-pyretics for fevers, intravenous and oral fluids for dehydration and dizziness, etc. Should a treating physician have any questions about how to treat symptoms related to talimogene laherparepvec or the study, he or she should be encouraged to speak with the PI or co-PI for guidance.

8.0 CORRELATIVES

A key finding in recent years is that treatment with OV initiates inflammation that facilitates cross-presentation of tumor antigens and the induction of local immune responses that are essential for therapeutic efficacy. Recent data demonstrated that OVs activate multiple subsets of dendritic cells (DC) to produce Type I IFN, pro-inflammatory cytokines and T cell co-stimulatory molecules that are key to driving innate and adaptive anti-tumor immune responses. However, limited information is available regarding the role of the immune response in dictating the course of peritoneal carcinomatosis after treatment with OV. In murine models, peritoneal metastatic ovarian and colorectal tumors foster an immunosuppressive, pro-tumor microenvironment that can be skewed toward protective anti-tumor responses using immunomodulatory agents. For example, CT26 peritoneal tumors attracted regulatory T cells (Treg), and treatment with a synthetic TLR7 agonist reduced Treg infiltration and bolstered CD8 T cell-mediated, a tumor-specific immunity[13]. Similarly, immunosuppressive (M2-type) macrophages were re-programmed to a protective M1-type in a peritoneal model of ovarian cancer by treatment with attenuated Listeria monocytogenes, a potent inducer of Th1-type immunity[14]. This is important information, because the immune content of human primary and metastatic CR tumors has been proposed as a reliable indicator of disease prognosis; for example a high ratio of CD8 T cells with a memory phenotype to regulatory T cells has been associated with good therapeutic outcome[15].

Interestingly, it was recently shown that immunity against peritoneal tumors is somewhat unique with regard to mechanisms of protection[16]. The peritoneal cavity harbors resident leukocyte types that are phenotypically and functionally distinct from their counterparts in other anatomic locations. These include B-1b cells[17], peritoneal NK cells[18], and peritoneal macrophages[19]. The functions of these cells in immunity against tumors of the peritoneal cavity is largely unexplored. This exploratory aim is innovative in that we will seek to elucidate changes in the peritoneal tumor immune microenvironment after treatment with different doses of talimogene laherparepvec. This information will facilitate the rational design of combination therapies to target anti- and pro-tumor immune effectors that are relevant to PSD of gastrointestinal, fallopian tube, ovarian, and primary peritoneal cancers.

8.1 Tumor Tissue Biomarkers

Archived formalin fixed paraffin embedded (FFPE) tumor tissue will be collected for all subjects at the end of the study, upon request from the PI (if available). Refer to *Study Manual* for collection, processing, and submission details.

Archived FFPE tumor tissue will be collected and sent to [name] Laboratory at Louisiana State University (LSU). It will be tested by IHC to evaluate T-cell immune infiltration status, the primary biomarker endpoints for this study. Expression of additional proteins that may be associated with

sensitivity or resistance to the treatment, include but not limited to, CD8, CD3, CD4, PD-L1 and FoxP3. Additionally, NanoString PanCancer Immune profiling RNA panel will be utilized to investigate differential immune gene expression in FFPE samples.

8.2 Immune Cells

Peripheral blood and peritoneal washings will be collected for immune cells from each subject at the following timepoints: baseline (prior to seroconversion dose on C1D1), prior to treatment on C2D1, prior to treatment on C4D1, and 30-day off treatment follow-up. If the subject comes off treatment mid cycle, take an additional plasma sample at the time of disease progression or off treatment. Refer to *Study Manual* for collection and submission details.

Peritoneal immune cells will be processed and stored by the Duke Immune Profiling Core facility under the direction of [name]. Peripheral blood immune cells will be processed and stored by the Substrate Services Core and Research Support (SSCRS) laboratory. All samples will be transferred for analysis to [name] at LSU. Polychromatic flow cytometry (PFC) panels will be used to compare treatment related changes in both tumor and peripheral immune cell compartments. Up to 50 markers may be analyzed using 3 PFC panels: 1) a 12-color 'Exhaustion Panel', 2) a 12-color 'Tumor Reactive T Cell Panel', and 3) a 14-color regulatory T cell (Treg) and monocytic myeloid-derived suppressor cells (m-MDSC) panel. This analysis will be overseen by [name].

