5.1 Screening Period

During the Screening Period, subjects are consented and screened for the study. Informed consent must be obtained before initiation of any screening procedure that is performed solely for the purpose of determining eligibility for this study. Evaluations performed as part of routine care before informed consent can be considered as screening evaluations if done within the defined screening period, and if permitted by the local Institutional Review Board (IRB) / Independent Ethics Committee (IEC) policies. Study eligibility is based on meeting all of the inclusion criteria and none of the exclusion criteria (refer to [Section 4.0](#)) before the first dose of study drug on Cycle 1 Day 1.

The following study procedures must be done within 28 days prior to Cycle 1 Day 1:

- Demographics
- Medical and cancer history
- Concomitant medications
- Physical examination
- Abdominal measurement
- Height
- Vital signs and weight
- ECOG performance status
- Adverse event assessment (review of baseline symptoms)
- Tumor assessment (CT and/or MRI scans)
- Blood tumor marker, if clinically indicated (e.g., CEA or CA19-9)
- Whole blood (for pharmacogenomics) (may be collected pre-dose on Cycle 1 Day 1)
- Coagulation tests (must be done prior to catheter placement)
- Peritoneal catheter placement (must be placed after confirmation of eligibility)

The following study procedures must be done within 7 days prior to Cycle 1 Day 1:

- CBC with differential
- Chemistries including liver function tests (LFTs)
- Serum pregnancy test (only for women of childbearing potential)

Subject eligibility is determined using lab results obtained prior to peritoneal port placement and up to 7 days prior to Cycle 1 Day 1. The Screening Period ends upon placement of the peritoneal port or final determination that the subject is ineligible for the study. Patients with pre-existing peritoneal ports for standard of care treatment are eligible for participation. For these patients the Screening Period ends upon receipt of the first dose of study drug or final determination that the subject is ineligible for the study.

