5.2 Peritoneal Catheter Placement

After confirmation of patient eligibility, the peritoneal catheter must be placed prior to initiation of treatment. Catheter placement must occur on Day -4 (+/- 2 days) prior to C1D1.

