6.2.1 Storage and Handling

Talimogene laherparepvec should be stored protected from light and according to the storage and expiration information (where required) provided on the label that is affixed to the package containing the investigational product. Talimogene laherparepvec should be thawed per the instructions provided in the pharmacy manual. Vials should be checked for cracks or damage that may occur during the thawing process if not performed properly. Drug vials will be destroyed on site once Product complaint has been resolved. See Pharmacy Information Guide.**Special Instructions for Use and Handling**

Follow local institutional guidelines for handling and administration, personal protective equipment, accidental spills, and waste disposal.

- Wear protective gown or laboratory coat, safety glasses, or face shield and gloves while preparing or administering talimogene laherparepvec. Cover any exposed wounds before administering. Avoid contact with skin, eyes or mucous membranes.
- After placement of the IP catheter, there will be a gauze and occlusive dressing placed over the puncture site for 7 days. Replace dressing if it falls off during this time.
- Dispose of all materials that have come in contact with talimogene laherparepvec (e.g., vial, syringe, needle, any cotton or gauze) in accordance with local institutional procedures.
- In the event of an accidental occupational exposure to talimogene laherparepvec (e.g., through a splash to the eyes or mucous membranes) during preparation or administration, flush with clean water for at least 15 minutes. In the event of exposure to broken skin or needle stick, clean the affected area thoroughly with soap and water and/or disinfectant.
- Spills should be treated with a virucidal agent such as 1% sodium hypochlorite or Virkon®. All materials contaminated with talimogene laherparepvec must be disposed of in compliance with local institutional guidelines. Incineration is appropriate.
- Advise subjects to place used dressings and cleaning materials in a sealed plastic bag and dispose in household waste or return to study site depending on local guidance.

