8.6 Peritoneal Cytokine Levels

Peritoneal fluid will be collected at baseline (prior to seroconversion dose on C1D1), prior to treatment on C2D1, prior to treatment on C4D1, and 30-day off treatment follow-up. If the subject comes off treatment mid cycle, take an additional peritoneal fluid sample at the time of disease progression or off treatment.

These samples will be processed and stored by the Duke Immune Profiling Core under the direction of [name]. Supernatent will be transferred to the Duke Phase 1 Biomarker Laboratory under the direction of [name]. Aliquots from all samples will be retained by [name] for analysis, including but not limited to, IL1 β , IL2, IL4, IL5, IL6, sILR6R, sGP130, IL7, IL8, IL10, IL12, IL13, IL15, IL17A, IL17E, IL22, IL23, IFN γ , TGF β 1, and TGF β 2, but could include other markers that represent best science for this drug and involved signaling pathways. Remaining supernatent will be transferred to [name] lab at LSU for above mentioned viral load analysis via previously described PCR techniques.

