9.1.3 Correlative Endpoints

Viral load will be measured by number of copies/mL; patients are expected to have undetectable viral load at baseline and increased viral loads on treatment. Cytokine levels will be measured in pm/mL. For both of these endpoints logarithmic transformations will be used to achieve normality. Immune cell markers will be measured as percentage of subset cell types. Ninety percent (90%) confidence interval (CI) estimates of mean changes in viral load, cytokine levels, and immune markers from baseline will be constructed in the intent-to-treat population (n=12 No preliminary data are available for these endpoints.

The proportion of patients who achieve at least a 2-log change in viral load or cytokine level will be estimated. With 12 patients studied in the intent-to-treat population the 90% upper confidence bound (1-sided) for change in viral load is at most 0.185. The proportion of patients exhibiting at least a 2-log change in cytokine levels (positive or negative) can be estimated to within at most +/- 0.237 with 90% confidence. The proportion of patients exhibiting a change of at least 0.15 in magnitude will be estimated similarly for immune markers.

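### The pre-drug peritoneal sample falls 2 to 6 days after on-study catheter placement, so the pooled change from baseline cannot separate drug effect from recovery after the procedure

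*Combined protocol and SAP*

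**What the plan says.** **Placement.** Section 5.2 states: "Catheter placement must occur on Day -4 (+/- 2 days) prior to C1D1". The study calendar (Appendix C) gives the same window, Day -6 to Day -2. Section 5.1 also lists placement among the procedures of the 28 days before C1D1, but 5.2 and the calendar are the specific statements. Section 6.2.1 adds that after placement "there will be a gauze and occlusive dressing placed over the puncture site for 7 days".

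**Existing ports.** Section 5.1: "Patients with pre-existing peritoneal ports for standard of care treatment are eligible for participation". No cap or expected number is given.

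**Sampling.** Section 8.2 collects blood and peritoneal washings for immune cells at "baseline (prior to seroconversion dose on C1D1), prior to treatment on C2D1, prior to treatment on C4D1, and 30-day off treatment follow-up". Section 8.6 follows the same pattern for cytokines: "Peritoneal fluid will be collected at baseline (prior to seroconversion dose on C1D1), prior to treatment on C2D1, prior to treatment on C4D1". The calendar has no peritoneal sample at or before placement.

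**Analysis.** Section 9.1.3 says that 90% intervals for "mean changes in viral load, cytokine levels, and immune markers from baseline will be constructed in the intent-to-treat population", with n given as 12. Section 9.1.4 describes flow cytometry on peritoneal lavage from the same baseline, C2D1 and C4D1. Neither section splits or adjusts by port status, and 9.1.5 lists neither port status nor time since placement among the baseline characteristics. Section 8.2 nevertheless describes the changes as related to treatment. Section 3.1 describes a non-randomized, open-label trial, and there is no control group.

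**The concern.** A change from baseline in a single-arm trial can be read as a drug effect only if nothing else relevant changes between the two samples. Here something does. For a subject whose catheter is placed on study, the baseline comes within days of a procedure that enters the peritoneal cavity, and every later sample comes weeks after it. Time since the procedure and exposure to drug move together, so the data cannot tell them apart. A subject with an existing port contributes a different kind of baseline, and the two kinds are averaged.

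Exploratory objective 4 (change in peritoneal leukocytes) and the 9.1.3 intervals for peritoneal cytokines and immune markers rest on this contrast. Section 8.0 also wants to look at changes after different doses and to use them in designing combinations. With 3 to 6 subjects per dose level, an uneven mix of new and existing ports could resemble a dose effect.

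**Working it through.** **1. The plan's own precision figures.** For a proportion at n = 12 and p = 0.5:
- two-sided 90%: 1.645 × √(0.25/12) = 0.237, as stated in 9.1.3;
- one-sided 90%: 1.282 × √(0.25/12) = 0.185, as stated.

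Both reproduce and are not in dispute. They describe sampling error only and say nothing about a shifted baseline.

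**2. Timing.** Cycle 1 lasts 5 weeks and later cycles 2 weeks, so C2D1 is 35 days and C4D1 is 63 days after C1D1. With on-study placement 2 to 6 days before C1D1:
- baseline: 2 to 6 days after placement, within the 7-day dressing period;
- C2D1: 35 + 2 to 35 + 6 = 37 to 41 days;
- C4D1: 63 + 2 to 63 + 6 = 65 to 69 days.

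These are nominal days. The ±3-day visit window can bring C2D1 to 37 − 3 = 34 days. If a Day 0 is counted, every interval grows by one day.

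**3. Half-width for a mean change at n = 12.** t(0.95, 11 df)/√12 = 1.796/3.464 = 0.518 SD. That is 0.259 log10 at SD 0.5 and 0.518 log10 at SD 1.0. Section 9.1.3 says that no preliminary data exist, so both SDs are assumptions.

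**4. Bias under an assumed placement effect.** Suppose placement multiplies the C1D1 value k-fold in subjects with a new catheter and the effect has gone by the later sample. The bias in mean log10 change is then −(share of new catheters) × log10(k). It exceeds the half-width when log10(k) > half-width ÷ share:

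| New catheters | SD 0.5 | SD 1.0 |
|---|---|---|
| 12 of 12 | k > 1.8 | k > 3.3 |
| 9 of 12 | k > 2.2 | k > 4.9 |
| 6 of 12 | k > 3.3 | k > 10.9 |

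**5. Coverage by simulation.** Settings: 40,000 trials of n = 12, no drug effect, baseline raised by 0.25 to 1.0 log10 in new catheters, 0 to 6 existing ports, SD 0.5 to 1.0. The bias runs from −0.125 to −1.0 log10. The nominal 90% interval covers the true drug effect of zero in:
- 87% of trials in the mildest case (0.25 log10, 6 existing ports, SD 1.0);
- 68% in a middle case (0.5 log10, 3 existing ports, SD 1.0);
- about 0% in the most severe case (1.0 log10, no existing ports, SD 0.5).

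**6. Endpoints that are less exposed.** The proportion with a 2-log cytokine change moves far less. At SD 0.5 it stays at or below 2.3%. At SD 1.0 it goes from 4.6% to between 4.9% and 15.9%, the top value needing a ten-fold effect in all 12 subjects. Viral load is little affected because 9.1.3 expects it to be undetectable at baseline.

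**The case against.** **Size and direction are undocumented.** No section says that placement raises cytokines or draws in leukocytes, or that any such effect has settled by C2D1. This stands. A reader might infer that placement inflames the cavity and so hides a true rise or turns it into a fall. The documents do not support that, least of all for immune markers: 9.1.3 analyses them as percentages of cell subsets, and a subset percentage can move either way when other cells arrive.

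**A modest effect need not dominate.** A reader might also infer that a mere doubling swamps the interval. With all 12 catheters new, that requires an SD below 0.301/0.518 = 0.58 log10. At SD 0.5, two existing ports already bring the bias to 0.301 × 10/12 = 0.251, below the half-width of 0.259. This stands too, and it is why the table gives a range.

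**A wash at placement is not a clean baseline.** It precedes the presence of the catheter, uses a different access route, and leaves subjects with existing ports on C1D1. Whether it is feasible cannot be judged from the documents, since collection details are left to the Study Manual. It therefore should not replace the C1D1 baseline.

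**C2D1 to C4D1 does not answer the question.** By C2D1 a subject has had the seroconversion dose and the first cohort dose, so this contrast omits the change from before to after drug.

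**The analyses are exploratory and descriptive.** That limits the priority. It does not supply the missing separation of drug and procedure.

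**Conclusion.** The confounding is real and follows from the schedule alone: a baseline 2 to 6 days after on-study placement, a next sample nominally 37 to 41 days after it, existing ports admitted without a cap, no control group and no split by port status. The pooled mean change in peritoneal cytokines and immune markers therefore cannot be attributed to drug alone.

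This is a limit on interpretation, not a measured error. The magnitudes depend on the assumed k, SD and share of new catheters, and on the effect having faded by the later sample. They show that the bias could range from slight to larger than the whole interval half-width. The primary safety objective and the MTD are not touched; viral load and the 2-log cytokine proportion are much less exposed than the mean change.

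**What to change.** - **Section 9.1.5:** add port status (placed on study or pre-existing) and days from placement to C1D1 to the baseline characteristics.
- **Sections 9.1.3 and 9.1.4:** beside the pooled estimate, report change from baseline in peritoneal cytokines and immune markers separately for new and pre-existing catheters. State that the pooled change is not attributable to drug alone.
- **Supplement:** show the C2D1-to-C4D1 change, labelled as a comparison of two samples that both follow dosing.
- **Optional:** where feasible, take a peritoneal wash at on-study placement as an additional value, keeping C1D1 as the baseline.

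**Cost.** The first three items need two recorded variables and some extra descriptive output, with no new sampling. The optional wash is one extra specimen at a procedure that already takes place. The drawback is small groups: splitting 12 subjects by port status may leave only a few in one group, so the split should be descriptive, without a formal comparison.
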